- 59 • HbA1c, questionnaires, insulin, and other analyses will include all subjects with any
 60 amount of corresponding data following CGM initiation.
- 61 • The tabulations of the safety outcomes will include all participants who enrolled,
 62 regardless of how much data is available.

63 **7 Analysis of Study Endpoints**

64 **7.1 Calculation of CGM Metrics**

65 **7.1.1 Calculation of 13 Week CGM Metrics**

66 All CGM metrics listed in Section 5 will be calculated on a 13-week period for each subject
 67 level. The windows for the 13-week periods are defined as follows:

Time Point	Window
1-13 Weeks	0 to 91 days after the CGM initiation date
14-26 Weeks	92 to 183 days after the CGM initiation date
27-39 Weeks	184 to 274 days after the CGM initiation date
40-52 Weeks	275 to 365 days after the CGM initiation date

68
 69 For each 13-week period, CGM metrics will be calculated by pooling all CGM readings
 70 occurring from 12:00 AM on the first day of the 13-week period up until 11:59PM on the last
 71 day of the 13-week period. For the first 13-week period, the first CGM reading will be the start
 72 datetime of the period. If a participant discontinues CGM prior to the last day of the 13-week
 73 period, then CGM data will include readings up to the last CGM reading on the discontinuation
 74 date. Calibrations will be excluded from all these calculations. CGM metrics for 13-week periods
 75 with less than 168 hours of CGM data will be set to missing.

76 Baseline CGM metrics will be calculated by pooling all blinded CGM readings up to 90 days
77 prior to the date of CGM initiation for each subject. Baseline CGM metrics with less than 72
78 hours of CGM data will be set to missing.

79 The amount of time using the CGM will be calculated as the number of CGM values multiplied
80 by the expected CGM measurement frequency (i.e., 5min in general), with the exception that
81 there can only be one value within the CGM measurement frequency. Percentage of time CGM
82 is used will be calculated as the amount of time using the CGM divided by the total possible time
83 the participant could have used the CGM during the same period. Note that this denominator
84 includes sensor warm-up periods with no CGM values, so this metric will serve as a conservative
85 estimate of CGM use.

86 **7.1.2 Calculation of 4 Week CGM Metrics**

87 All CGM metrics listed in Section 5 also will be calculated on a 4-week interval for each subject.

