7.4 Statistical Methods

For all outcomes, summary statistics appropriate to the distribution will be tabulated on a subject level overall and within the subgroups defined in Section 12. For the CGM metrics, summary statistics appropriate to the distribution also will be tabulated for each 4-week interval and for the first and last 26 weeks of the study. For the questionnaires, summary statistics will be reported for the mean scores in addition to the individual responses for each question.

For all outcomes, a linear mixed model with a random subject effect will be used to test whether the mean change from baseline significantly differs from zero. These models will be fit for each of the subject level CGM metrics and HbA1c at 13, 26, 39, and 52 weeks. They also will be fit for the questionnaires at 26 and 52 weeks. If values are skewed, then winsorization will be utilized. Point estimates and 95% confidence intervals for change in glycemic outcomes will be reported.

For the three mental health screening questionnaires, only summary statistics will be tabulated. The three mental health screening questionnaires falling under this umbrella are the Patient

187 Health Questionnaire-8, the Diabetes Distress Scale (Management Distress Subscale), and the
188 Fear of Hypoglycemia Survey (Worry Subscale).

189 **7.5 Analyses Windows**

190 For HbA1c, only measurements occurring within ± 45 days of the target measurement date at a
191 given time point will be included in the tabulation of summary statistics. The windows for
192 glycemic metrics were defined above in Section 7.1.

193 **7.6 Sensitivity Analyses**

194 For CGM and HbA1c outcomes, a complete-case analysis restricting to non-missing outcomes
195 will also be assessed. A paired t-test (for normally distributed outcomes) or a Wilcoxon signed
196 rank test (for skewed outcomes) will be used.

197 **8 Safety Analyses**

198 All adverse events that occur on or after the date of enrollment will be listed in a table.

199 For events occurring on or after the date of CGM initiation, the reported safety outcomes include
200 diabetic ketoacidosis (DKA), severe hypoglycemia (SH), hospitalization, and emergency room
201 visits. The following statistics will be tabulated for each safety outcome:

- 202 • Total number of events
- 203 • Number and proportion of subjects with an event (discretized into bins)
- 204 • Incidence rate per 100 person years

205

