206 The number of person-years for the incidence rate calculations will be inclusively defined as the
207 number of person-years in between the CGM initiation date and the last day of study follow-up
208 (completion date, withdrawal date, etc.).

209 **9 Adherence and Retention Analyses**

210 **9.1 Protocol Adherence**

211 The number of and reasons for participant contacts with the virtual clinic will be reported in a
212 table to assess protocol adherence for the study.

213 **10 Baseline Descriptive Statistics**

214 Baseline demographic and clinical characteristics of the cohort of all subjects who initiate the
215 CGM and were included in the glycemic analyses will be summarized in a table. Use of
216 medications and non-insulin therapy will also be reported. For continuous variables, summary
217 statistics appropriate to the distribution will be given. For discrete variables, number and
218 percentage will be reported for each category. Summary statistics for demographics and clinical
219 characteristics will be presented overall, by diabetes type, by insulin modality, by whether the
220 participant was seeing an endocrinologist or a primary care provider at baseline, by baseline
221 HbA1c groups ($<7.5\%$, 7.5% to $<9.0\%$, and $\geq 9.0\%$), and by age (<25 , $25\text{-}65$, and >65 years). Cut
222 points for age and baseline HbA1c may be reassessed after data are collected.

223 **11 Planned Interim Analyses**

224 No formal interim analyses or stopping guidelines are planned for this study. Data will be
225 monitored on an ongoing basis including:

- 226 • Status of enrolled participants
- 227 • Recruitment rates by month and by site
- 228 • Baseline demographic and clinical characteristics
- 229 • Dropped participants and reasons for discontinuing
- 230 • Reportable adverse events

231 **12 Subgroup Analyses**

232 Subgroup analyses for % of time using the CGM, % time in range, % time >180 mg/dL, % time
233 <70 mg/dL, and HbA1c will be performed based on the following factors:

- 234 • Baseline HbA1c (categorized as <7.5%, 7.5% to <9.0%, and ≥9.0%)
- 235 • Insulin modality
- 236 • Age (categorized as <25, 25-65, and >65)
- 237 • Type of healthcare provider (endocrinologist or primary care provider)
- 238 • Diabetes Duration (categorized as <5, 5-<10, 10-<20, ≥20)
- 239 • Race/Ethnicity
- 240 • Household income (categorized as <\$50,000, \$50,000-<\$100,000, and ≥\$100,000)

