241 For continuous variables, results will be displayed in subgroups based on cut points although the
242 analysis will utilize the variable as continuous. Cut points for age, baseline HbA1c, diabetes
243 duration, and household income may be reassessed after the data are collected.

244 Within each subgroup, summary statistics will be tabulated. P-values for change from baseline
245 will be calculated within each subgroup using a linear mixed model will be performed as
246 described in Section 7.4.

247 Percentage of CGM discontinuations will also be tabulated by the factors listed above.

248 **13 Multiple Comparisons**

249 No adjustments for multiple comparisons will be made.

250 **14 Additional Analyses**

251 CGM metrics over 13-week periods will be tabulated on a subject level by time of day. In these
252 analyses, daytime will be defined as 6:00 AM to <12:00 AM and nighttime will be defined as
253 12:00 AM to <6:00 AM. For this analysis, CGM metrics will only be calculated if the participant
254 has at least 126 hours of CGM data during daytime and at least 42 hours of CGM data during
255 nighttime.

256 Total scores for questionnaires in Section 7.2 will be stratified by number of mental health
257 service sessions. Additional analyses will be conducted to assess the bivariate relationship
258 between questionnaire responses and glycemic metrics at 26 and 52 weeks. These relationships
259 will be assessed by displaying scatterplots, along with the corresponding Spearman correlation

260 coefficient. A 95% confidence interval for the Spearman correlation coefficient will be reported.
261 In these analyses, the following relationships will be explored:

262 • % Time <70 mg/dL vs. Fear of Hypoglycemia Worry Subscale Mean Score
263 • % Time <70 mg/dL vs. Hypoglycemia Confidence Survey Mean Score
264 • % Time in Range vs. Glucose Monitoring Satisfaction Survey Mean Score
265 • % Time in Range vs. Diabetes Distress Scale Management Distress Subscale Mean Score
266 • CGM use at 26 weeks vs. Diabetes Technology Attitudes Survey Mean Score

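### Change-from-baseline tests on CGM use compare follow-up with a short study-assigned blinded wear, so their p-values say nothing about a change in CGM use

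*SAP*

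**What the plan says.** SAP Section 5 lists percentage of time using the CGM and hours of CGM use as separate outcomes. Section 7.1.1 defines the percentage among the CGM metrics.

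- **Overall test (SAP 7.4).** "For all outcomes, a linear mixed model with a random subject effect will be used to test whether the mean change from baseline" differs from zero. On scope: "These models will be fit for each of the subject level CGM metrics and HbA1c at 13, 26, 39, and 52 weeks".
- **Sensitivity test (SAP 7.6).** A paired t-test or signed rank test is planned for CGM and HbA1c outcomes.
- **Subgroups (SAP 12).** The outcome list opens "Subgroup analyses for % of time using the CGM, % time in range, % time >180 mg/dL, % time" and ends with time below 70 mg/dL and HbA1c. Then: "Within each subgroup, summary statistics will be tabulated. P-values for change from baseline" follow, using the Section 7.4 model.
- **Exemption (SAP 7.4).** There is one: "For the three mental health screening questionnaires, only summary statistics will be tabulated".
- **Baseline (SAP 7.1.1).** "Baseline CGM metrics will be calculated by pooling all blinded CGM readings up to 90 days" before initiation. Baseline metrics resting on less than 72 hours of data are set to missing.
- **Definition of use (SAP 7.1.1).** Percentage of time CGM "is used will be calculated as the amount of time using the CGM divided by the total possible time" available in the same period. No denominator is given for the baseline period.
- **Who has a baseline.** The SAP eligibility table excludes real-time CGM use in the last 12 months. Protocol 2.7 assigns non-users one blinded sensor wear, usually at least 10 days.

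**The concern.** A change from baseline is informative when both ends measure the same thing. For glucose metrics they do: the blinded wear samples glucose before the intervention. For CGM use they do not. At follow-up, the percentage records how much a person chose to wear a sensor whose readings they could see. At baseline, it records whether they completed a required wear of a sensor whose readings were hidden. Under the SAP criteria nobody has recent real-time use for the blinded wear to stand in for.

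CGM use is a listed efficacy outcome in Protocol 6.3, and the study's stated aim covers feasibility and ongoing CGM use. A table showing a highly significant change in use, in either direction, could be read as evidence about uptake or decline when it is neither.

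**Working it through.** The plan gives no figure to reproduce: the sample of 300 is declared a convenience sample, and no alpha, SD or expected level of use is stated. The check asks what number the written rule produces.

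**1. Baseline percentage under the two denominators the text leaves open**

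- Wear-period denominator: recorded time divided by the length of the blinded wear. The value is not in the documents. I assume 95%, with 97% as an alternative.
- 90-day denominator: 10 days / 90 days = 11.1%. The range is 72 h / (90 × 24 h) = 3.3% at the SAP minimum, to 20 / 90 = 22.2% with two 10-day wears.

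**2. Change = follow-up use minus baseline use, in percentage points (follow-up values assumed)**

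| Follow-up use | Baseline 95% of wear | Baseline 97% of wear | Baseline 11.1% of 90 days |
|---|---|---|---|
| 60% | -35 | -37 | +48.9 |
| 85% | -10 | -12 | +73.9 |
| 95% | 0 | -2 | +83.9 |

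**3. What the test would report**

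Assume follow-up use of 85% with SD 20, and baseline SD 4 (wear period) or 3 (90 days), independent of follow-up. Then t = change / (√(SD² + SD_baseline²) / √n).

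- n = 300, wear period: -10 / (√416 / √300) = -10 / 1.178 = -8.5.
- n = 300, 90 days: 73.9 / (√409 / √300) = 73.9 / 1.168 = +63.3.
- n = 50 (the Protocol 2.1 goal for each of the youngest and oldest age groups), wear period: -10 / 2.884 = -3.5, p about 0.001.
- n = 50, 90 days: 73.9 / 2.860 = +25.8.

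The same behaviour could thus be reported as a significant fall or a very large rise. Neither result describes a change in personal CGM use.

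**4. Hours of use**

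If hours are totalled over the period, a 10-day wear caps the baseline at 10 × 24 = 240 h. The first follow-up window (days 0 to 91) holds up to 92 × 24 = 2,208 h. Any follow-up use above 240 / 2,208 = 10.9% then exceeds that cap, purely because the windows differ in length.

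**5. How many such p-values**

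Section 12 gives 3 HbA1c, 3 age, 2 provider, 4 duration and 3 income levels. With an assumed 2 insulin modalities that is 17, leaving out race/ethnicity. At four time points this makes 17 × 4 = 68 p-values for percentage use alone, or 136 if also split by the two diabetes types, as SAP Section 3 suggests.

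**The case against.** The strongest reply is that the plan never seriously meant to test change in use. Section 7.4 promises change estimates and confidence intervals only for glycemic outcomes. Section 6.1 gives CGM use its own cohort. The reference to all outcomes cannot be literal, because Section 5 also lists a survey given only to people who stop CGM. The table shells are in a separate document that is not available here. Those are fair hints about intent, but they exempt nothing: Section 12 names percentage use among five outcomes and attaches the change p-value to them without distinction.

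Other parts of the reply stand and limit the point:

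- A reader might infer that baseline use is zero, so that significance is guaranteed. That is not the SAP's rule: a participant with under 72 hours of blinded data has a missing baseline, not a zero.
- The 90-day denominator is a strained reading. The 90 days limit which readings are pooled, and the stated denominator is time the participant could have used the CGM. The wear period fits that text better. Under that reading the contrast is still uninformative, but its sign is less open.
- A reader might infer that the sign depends only on the definition. It also depends on the assumed levels of use: above 95% at follow-up, the change is positive against both the 95% and the 11.1% baselines.
- A reader might infer that subgroup differences in use are not tested at all. Section 12 says the analysis will treat continuous factors as continuous, which implies some model across the factor. The sentence names no test and leaves out categorical factors, so the fair criticism is that the comparison is not spelled out.
- A reader might extend the point to the CGM benefit and barrier scores. The documents do not support that: those items ask for agreement with statements about wearing a CGM, on which non-users can hold views.

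The current protocol also admits some current CGM users, who could have a genuine baseline. The SAP baseline rule uses blinded readings only, so shared personal CGM data have no place in it.

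**Conclusion.** The point holds in this limited form. As written, SAP 7.4, 7.6 and 12 apply change-from-baseline tests to percentage and hours of CGM use. For participants who meet the SAP criteria, the baseline is compliance with an assigned blinded wear, so the resulting p-values are uninformative. This conclusion rests on the text alone.

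The size of the artefact rests on assumptions. At 85% follow-up use it runs from about -10 points (95% of the wear period) to about +74 points (11% of 90 days). The reversal of sign is an illustration under those values, not a general result.

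The consequence is small. All analyses are exploratory, there is no primary outcome, and the planned summaries of use by period and subgroup are unaffected. It is a desirable clarification and does not threaten the study's conclusions.

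**What to change.** Amend the SAP in three places:

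1. In Sections 7.4, 7.6 and 12, state that percentage and hours of CGM use are exempt from change-from-baseline testing, next to the existing exemption for the three mental health screeners.
2. For these two outcomes, report the level in each follow-up period with a 95% confidence interval, overall and by subgroup. The summary statistics are already planned, so only the interval is new.
3. In Section 12, state explicitly that levels of use will be compared across the subgroup factors, with continuous factors modelled as continuous, as that section already indicates, and categorical factors compared between their levels.

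The cost is SAP wording and matching edits to the table shells. No new data, visits or participants are needed.

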112 document, with the ethical principles that have their origin in the Declaration of Helsinki, with  
113 the protocol described herein, and with the standards of Good Clinical Practice (GCP).

114 **Chapter 2: Study Enrollment and Baseline Data Collection**

115 **2.1 Participant Recruitment and Informed Consent**

116 Adults (age  $\geq 18$  years) with type 1 diabetes or type 2 diabetes using insulin therapy (Tidepool-  
117 compatible pump or injections) will be enrolled. Although the primary focus of the study is to  
118 enroll non-CGM users, CGM users whose glycemic control is suboptimal can be enrolled.  
119 Participation will be limited to U.S. residents in states where the virtual clinic is licensed; state  
120 eligibility will be verified as part of screening. Potential participants may be recruited through  
121 insurance providers, primary care networks, or health care providers. Potential participants also  
122 may become aware of the study by other means, such as another study participant.

123 Up to 800 individuals may sign the informed consent form to initiate screening. Enrollment will  
124 proceed with the goal of at least 300 participants initiating training for CGM use with the Virtual  
125 Clinic. The goal will be to limit T2D enrollment to no more than 100. Recruitment efforts will be  
126 focused on participants who receive diabetes care in a primary care setting rather than through an  
127 endocrinologist, with a goal of having at least 225 who have not seen an endocrinologist in the  
128 past six months. Eligible participants will be included without regard to gender, race, or  
129 ethnicity.

130 The goal will be to include at least 50 participants  $<25$  years of age and at least 50 participants  
131  $>65$  years of age.

132 **2.1.1 Informed Consent and Authorization Procedures**

133 Individuals who indicate that they are interested will be directed to a website with information  
134 about the study. Interested individuals will be able to communicate with study staff who can  
135 answer questions about the study as part of the informed consent process. Individuals who want  
136 to participate in the study will sign the Institutional Review Board (IRB) approved electronic  
137 consent form. As part of the informed consent process, each participant will be asked to sign an  
138 authorization for release of personal information. Participants will be asked to sign an addendum  

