173 9. Participation in a different diabetes management study during the study  
174 10. Planned relocation to a state other than current state of residence during the study if virtual  
175 clinic is not licensed in the new state.

176 *Individuals working routinely in a state other than current state of residence in the next six  
177 months are also ineligible if the virtual clinic is not licensed in that state.*

178 **2.4 Screening Procedures**

179 Participants will be asked to confirm eligibility by completing a screening questionnaire.  
180 Participants who pass screening will be asked to provide baseline data. Current CGM users will  
181 also be asked to share their CGM data to confirm eligibility. If current data cannot be shared,  
182 current CGM users will be asked to complete blinded CGM data collection. Non-CGM users  
183 will also be asked to complete blinded CGM data collection. Participants will be asked to submit  
184 a baseline HbA1c sample

185 **2.5 Collection of Baseline Data and Testing**

186 After informed consent is signed, baseline data will be collected, including the following:

187 • Contact information  
188 • Date of birth

189 • Demographics  
190 • Height and weight  
191 • Socio-economic information such as education, income, and insurance  
192 • Name and contact information of healthcare provider for diabetes management  
193 • Diabetes history, including diabetes duration, prior management, insulin delivery method,  
194 meal bolus determination method, prior severe hypoglycemia (SH), prior diabetic  
195 ketoacidosis (DKA)  
196 • Medical history  
197 • Medications, including but not limited to medications other than insulin being used for  
198 glycemic control  
199 • Prior CGM experience and knowledge, including why CGM is not used  
200 • General health  
201 • Questionnaires (see Chapter 4)  
202 • Finger stick to measure HbA1c  
203 • Blinded CGM Data Collection

204 **2.5.1 HbA1c**

205 HbA1c will be measured at a central laboratory. The participant will be sent a kit, which will  
206 include a blood collection tube and shipping materials, to obtain a finger stick blood sample. The  
207 sample will be returned to the lab in a prepaid mailer. Participants will be able to view their  
208 HbA1c results through the study website.

209 **2.6 CGM System**

210 Participants will use the Dexcom G6, which is a commercially available CGM system. CGM  
211 data will be shared with CDCES and study team members.

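### The subgroup p-values in SAP section 12 test change within each subgroup, so they cannot show that change differs by factor, and in the outer baseline-HbA1c groups they are distorted by regression to the mean

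*SAP*

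**What the plan says.** SAP section 12 lists seven subgroup factors and five outcomes, HbA1c among them. Its inferential statement reads "Within each subgroup, summary statistics will be tabulated. P-values for change from baseline" and refers to section 7.4 for the mixed model to be fitted in each subgroup. Section 7.4 in turn says: "For all outcomes, a linear mixed model with a random subject effect will be used to test whether the mean change from baseline significantly differs". The comparison value there is zero, and that model has no subgroup factor. Neither SAP 7.4, SAP 12 nor Protocol 6.6 names an interaction or any other between-subgroup comparison.

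Just before the p-value sentence, section 12 says that for continuous factors the cut points serve for display, although the "analysis will utilize the variable as continuous". It gives no model, term or p-value for that analysis, and it allows the cut points to be reassessed once data are in.

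One factor is "Baseline HbA1c (categorized as <7.5%, 7.5% to <9.0%, and ≥9.0"%). Protocol 2.4 asks for "a baseline HbA1c sample", so one measurement both assigns the group and starts the change. The study has a single arm. SAP section 3 stratifies analyses by diabetes type, and SAP section 1 calls all analyses exploratory.

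**The concern.** A subgroup analysis is normally read as an answer to who benefits more. A test of change against zero, run separately in each subgroup, does not address that. With equal benefit everywhere, a large group tends to reach significance and a small one may not, and the contrast is easily mistaken for a difference in effect.

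For HbA1c change by baseline HbA1c there is a second problem. People placed in the top group by one measurement tend to have a lower value next time, and those in the bottom group a higher one, whatever the virtual clinic does. With no control arm, nothing in the design separates that drift from a treatment effect, and the SAP does not mention it. What is at stake is any statement about which participants gain from the clinic.

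**Working it through.** The plan has no figure to reproduce: 300 is described as a convenience sample, and no SD, correlation, effect size or alpha is given. The calculations below use assumed inputs. Alpha is taken as two-sided 0.05, from the nonzero alternative in SAP section 3 and the 95% intervals in SAP 7.4.

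**1. Within-subgroup p-values and group size**

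- Assumed: the same true fall of 0.3 HbA1c points in both groups; SD of change 0.58 to 1.0. The SD range follows from SD of change = SD × √(2(1 − r)): SD 1.3 with r 0.9 gives 0.58, and SD 1.6 with r 0.8 gives 1.01.
- Group sizes: Protocol 2.1 says "The goal will be to include at least 50 participants" under 25 years, and likewise over 65. With 300 in total, 300 − 50 − 50 = 200 remain. These are minimum goals, used here only to show the effect of size.
- Power = Φ(0.3 × √n / SD − 1.96).

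| n | SD of change | 0.3√n / SD | Power | Missed |
|---|---|---|---|---|
| 50 | 0.58 | 3.66 | 96% | about 5% |
| 50 | 1.0 | 2.12 | 56% | 44% |
| 200 | 0.58 | 7.32 | >99.9% | <0.1% |
| 200 | 1.0 | 4.24 | 99% | 1% |

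Analyses are stratified by diabetes type and type 2 enrollment is to be held to about 100, so real cells are smaller. If two thirds of each group fell in one type (33 and 133) and the SD were 1.0, power would be 41% and 93%.

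**2. Regression to the mean in the baseline-HbA1c groups**

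- Assumed: normal HbA1c with mean 8.0 to 8.6, SD 1.3 to 1.6, baseline to follow-up correlation r 0.8 to 0.9, and no true change.
- Expected change in a group = −(1 − r) × (group mean − overall mean), with group means from the truncated normal distribution.
- Worked case (mean 8.3, SD 1.6, r 0.8): group means are 6.47 for <7.5%, 8.25 for 7.5 to <9.0%, and 10.05 for ≥9.0%. Expected changes are −0.2 × (6.47 − 8.3) = +0.37, −0.2 × (8.25 − 8.3) = +0.01, and −0.2 × (10.05 − 8.3) = −0.35.
- Over the whole range: <7.5% rises 0.14 to 0.41; the middle group moves −0.05 to +0.07; ≥9.0% falls 0.13 to 0.39.
- In the worked case with 200 participants, roughly the type 1 stratum, each outer-group test would be significant about 84% of the time with no true change.

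**3. Would a plain interaction test cure the baseline-HbA1c problem?**

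No. In the worked case the gap in change between the outer groups is 0.37 + 0.35 = 0.72 points, or 0.36 at r 0.9. With 200 participants, a simple test of that gap would be significant about 99% and 82% of the time respectively, with no true difference.

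**The case against.** The strongest reply is that section 12 treats continuous factors as continuous. That makes no sense for a within-category test against zero, so some analysis across the factor is evidently intended. This stands in part. A reader might infer that the plan ignores between-subgroup comparison altogether, and the text does not support that for age, diabetes duration and baseline HbA1c, or possibly income. For these factors the fault is an undefined analysis that conflicts with the paragraph after it. The sentence cannot help insulin modality, provider type or race/ethnicity.

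A reader might also infer that all baseline-HbA1c groups change through regression to the mean alone, or that the bottom group will be reported as worse. Neither follows. The middle group barely moves, and any true effect adds to the drift. A uniform true fall of 0.3 would leave the bottom group between −0.16 and +0.11 and the top group between −0.43 and −0.69.

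The 44% miss rate belongs to the upper end of the assumed SD and should not be quoted without the range.

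Finally, the SAP never says that these p-values will show differences between subgroups. It has no primary outcome, and section 7.4 already promises estimates with 95% intervals for glycemic change. This lowers the severity. It does not make the stated p-values informative about differences.

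**Conclusion.** The concern holds with these limits. The only subgroup inference spelled out cannot show whether change differs by factor. That is complete for the three categorical factors; for the continuous ones it is a matter of missing specification and internal conflict.

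The size rests on assumptions, because the documents give no SD or correlation. With an identical 0.3-point fall, a group of 50 misses it in about 5% to 44% of cases against about 1% or less for a group of 200, and smaller cells within diabetes type do worse. The outer baseline-HbA1c groups drift by roughly 0.13 to 0.41 points in opposite directions with no effect at all. Severity is low to moderate, since every analysis is exploratory.

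**What to change.** Amend SAP section 12 as follows.

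- Within diabetes type, replace the within-subgroup p-values with a factor-by-visit term in the mixed model for each factor and outcome. Enter age and diabetes duration as continuous, and state the model for income.
- Report the difference in change with its 95% confidence interval. Show subgroup estimates with 95% intervals and no p-values.
- For HbA1c change by baseline HbA1c, use neither within-group tests nor a plain interaction test. Either report it descriptively with a regression-to-the-mean caveat, or use a method that allows for it, such as change against the average of baseline and follow-up, or a reliability correction over a stated range. Grouping by baseline CGM glucose would lessen the artefact but not remove it.

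The cost is SAP wording only, with no new data or visits. The downside is low power in small groups. With an SD of change of 1.0 and 150 versus 50 participants, a difference in change of 0.3 points is detected with power Φ(0.3 / √(1/150 + 1/50) − 1.96) = Φ(−0.12) = 45%; with 100 versus 100 it is 56%. A non-significant term should therefore be read from its interval and not as evidence of equal benefit.
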